7.2.3 PRODUCT STORAGE AND STABILITY

Mycophenolate Mofetil (MMF)

MMF has demonstrated teratogenic effects in rats and rabbits, therefore MMF tablets should not be opened or crushed. Avoid inhalation or direct contact with skin or mucous membranes of the powder contained in MMF tablet/capsules.

Pegloticase

Before preparation for use, pegloticase will be stored in the carton, maintained under refrigeration between 2°C and 8°C (36°F and 46°F), protected from light, and will not be shaken or frozen. Investigational clinical supplies will be received by a designated person at each study site, handled and stored safely and properly, and kept in a secured location to which only the Investigator and designated assistants have access. Clinical supplies will be dispensed only in accordance with the protocol. We will keep accurate records of the clinical supplies received and, the amount dispensed for each participant, and the amount remaining at the conclusion of the study. We will mark the label of any vials that are not to be used with a large "X," and document the reason for rejecting them on the drug accountability log. In accordance with good pharmacy practice, gloves will be worn during preparation of the dose.

7.2.4 PRODUCT DESTRUCTION

The study sites will maintain an inventory of drug supplies received and dispensed. UAB will provide forms to document all inventory transactions. Upon completion or termination of the study, all unused drug supplies, will be destroyed with written certification confirming destruction within sixty (60) days of study completion or expiration of the study drug.

7.2.5 PREPARATION

Mycophenolate Mofetil (MMF)

Mycophenolate Mofetil (MMF) capsules include croscarmellose sodium, magnesium stearate, povidone (K-90) and pregelatinized starch. The MMF capsule shells contain black iron oxide, FD&C blue #2, gelatin, red iron oxide, silicon dioxide, sodium lauryl sulfate, titanium dioxide, and yellow iron oxide. All MMF capsules will be over-encapsulated with cellulose to match compounded placebo. Favorable pharmacokinetic properties of the encapsulation process have been consistently noted with other substances.

Pegloticase

Pegloticase vials will be visually inspected for particulate matter and discoloration before administration, whenever solution and container permit. Vials will not be used if either is present. Using appropriate aseptic technique, 1 mL of pegloticase will be withdrawn from the vial into a sterile syringe. Any unused portion of product remaining in the vial will be discarded. Syringe contents will be injected into a single 250 mL bag of 0.45% or 0.9% Sodium Chloride Injection, United States Pharmacopeia (USP) for IV infusion and will not be mixed or diluted with other drugs. The infusion bag containing the dilute pegloticase solution will be inverted a number of times to ensure thorough mixing, but will not be shaken. Pegloticase-diluted in infusion bags is stable for 4 hours at 2°C to 8°C (36°F to 46°F) and at room temperature (20°C to 25°C, 68°F to 77°F); however, the diluted solution will be stored under refrigeration, not frozen, protected from light, and used within 4 hours of dilution. Before administration, the diluted solution of pegloticase will be allowed to reach room temperature. Pegloticase in a vial or IV infusion fluid will never be subjected to artificial heating.

7.3 MEASURES TO MINIMIZE BIAS: RANDOMIZATION AND BLINDING

Participants will be randomized 3:1 to either pegloticase + MMF (Peg+MMF) or to pegloticase + placebo (peg+PBO). Randomization allocation will be balanced in time and by site to achieve 24 peg+MMF and 8 peg+PBO using a double-blind design. Treatment assignment will be determined by a random number generator and stratified by site using a central randomization system to ensure the 24/8 allocation. If any concerns arise during the randomization procedures, both the pharmacist and study coordinator will contact the Data Coordinating Center (DCC) at UAB. The UAB IDS will be responsible for assignment of randomization sequence. A drug log will be used to track the study drug from pharmacy to each randomized study participant. The centralized management of the medication will allow maintenance of a double-blind trial.

As all participants and study investigators will be blinded to treatment assignment. If there is a serious adverse event, then unblinding will be discussed and if deemed necessary to unblind the participant, then the ID of the unblinded participant, reasons for unblinding, name of the pharmacist and a list of whomever becomes unblinded will be kept in the study binder and centrally at the Data Coordinating Center and Central Pharmacy. The pharmacist will contact that participant's primary physician about the exposure. If necessary, the participant will be withdrawn from the study. NIAMS and the DSMB via KAI will be informed of any unexpected unblinding via email or at the scheduled DSMB meetings.

7.4 STUDY INTERVENTION COMPLIANCE

Adherence to the medication will be recorded by pill counts at the follow-up study visits and consumption of at least 80% will be required to consider the participant compliant. A non-compliant participant will continue in the study and enter analyses as mandated by statistician. Pill counts and infusion log will be used to calculate study intervention compliance. Other issues of non-adherence to study procedures will be reinforced with participants at study visits and recurrent non-adherence will lead to study discontinuation.

7.5 CONCOMITANT THERAPY

Concomitant medications are defined as drug or biological products other than the study drug(s) taken by a participant during the clinical trial. This includes other prescription medications (including preventive vaccines), over-the-counter medications, herbal medications, vitamins, and food supplements. A comprehensive list of participant's concomitant medications will be collected at baseline and at V2, V3, V5, V7-V17 each visit. This will include the name of the drug/vitamin/supplement, dose, route of administration, start and stop dates, and the reason for which the medication was taken. All medications will be listed by participant using the generic name(s) of the drug/vitamin/supplement. Serious adverse events related to the use of a concomitant drug/vitamin/supplement will be documented on the appropriate AE eCRF.

Prior to participation in RECIPE participants will be instructed to stop their current urate lowering therapy.

7.5.1 RESCUE MEDICINE

There is no specific rescue medication for mycophenolate adverse events. Overdose of MMF will be managed with prompt decontamination via activated charcoal, symptomatic management of nausea and vomiting along with adequate hydration.⁵⁴ Adverse effects associated with MMF are subsequently reviewed in section 8.3.3.3.

All participants will receive prophylactic treatment to reduce the risk of acute gout flares, unless medically contraindicated or not tolerated as noted in the FDA-approved pegloticase full prescribing information. The participant will begin a regime of colchicine (0.6mg/day) or Non steroidal anti-inflammatory drug prophylaxis at least 1 week before the first dose of pegloticase and it will continue for the duration of pegloticase therapy. Colchicine prophylaxis will not be interrupted during the course of the clinical trial unless medically contraindicated or if the participant becomes intolerant of colchicine, regardless of whether a gout flare occurs.

At the discretion of the investigator, patients still having insufficient relief with colchicine (0.6mg/day) or Non steroidal anti-inflammatory drug prophylaxis are allowed to take oral prednisone, prednisolone or equivalent at a dose up to 20 mg/day for a maximum of 7 days.

8 STUDY INTERVENTION DISCONTINUATION AND PARTICIPANT DISCONTINUATION/WITHDRAWAL

8.1 DISCONTINUATION OF STUDY INTERVENTION

Due to the risk of anaphylaxis and IRs being higher in patients who have lost therapeutic response, participants with two consecutive serum urate levels above 6 mg/dL shall be classified as a non-responder and discontinued from the study. Investigators will obtain a pre-dose serum urate sample for all patients and review results to verify the serum urate level is \leq 6 mg/dL prior to infusion.

Discontinuation from the study intervention does not mean discontinuation from the study, and remaining study

procedures should be completed as indicated by the study protocol. If a clinically significant finding is identified (including, but not limited to changes from baseline) after enrollment, the investigator or qualified designee will determine if any change in participant management is needed. Any new clinically relevant finding will be reported as an adverse event (AE).

The data to be collected at the time of study intervention discontinuation will include the following: If the study drug is discontinued, unless the subject withdraws consent, the participant will complete visit 17 (two weeks post discontinuation) and visits 17-20. If the participant doesn't want to continue with the follow-up visit schedule detailed above, then it is important to complete a close-out visit.

Based on the known safety profiles of pegloticase and MMF and the procedures we have in place, we believe it is very unlikely, but possible that we could witness one serious AE related to infection. We will institute a stopping rule for safety re-evaluation that would occur if we register more than one such serious adverse reaction (eg. infection that leads to hospitalization). We would then stop the study to comprehensively review safety and our study protocols in conjunction with the DSMB. Other serious adverse reaction or deaths may or may not be related to the study and stopping or discontinuation of the study will be considered on an individual basis. See **Appendix 9** Data Safety Monitoring Plan.

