3.2 BACKGROUND

Gout affects approximately 4% of the U.S. population, is the most common form of inflammatory arthritis in men, and is associated with decreased quality of life. The frequency of gout is increasing worldwide, with prevalence rates

estimated to be as high as 7% in older men, based on our work and the work of others. 10-12 It is estimated that up to 400,000 (up to 5% of the estimated 8 million persons with gout) in the United States experience chronic refractory gout, characterized by ongoing symptoms of active disease and a failure to control/maintain serum urate < 6 mg/dL with conventional xanthine oxidase inhibitors (i.e. allopurinol and febuxostat) and uricosuric agents (i.e. probenecid). 2,13-15 These patients often have significant, disabling urate deposits in soft tissues and bone known as tophi.

Figure 2. Urate reducing efficacy of pegloticase ¹

As stated in the study rationale (section 2.1), pegloticase has been associated with a high rate of infusion reactions (IRs) including anaphylaxis. IRs occurred in 26% of participants on pegloticase compared to 5% in placebo, and anaphylaxis

was reported in 5% of participants on pegloticase vs. 0% on placebo.⁵ Additionally, in one study the drug's immunogenicity leads to antipegloticase antibody (Ab) formation and associated loss of efficacy manifested by a rapid increase in serum urate levels in roughly 42% of all participants (n=212).^{5,16}

A relationship between the loss of urate-lowering efficacy (indicated by a rise in serum urate levels) and high-titer antibody formation was initially identified in a post-hoc analysis of two studies. ^{1,5} Participants with high anti-pegloticase antibody titers (>1:2430) experienced a significant loss of pegloticase activity that was attributed to more rapid clearance of drug in the presence of these antibodies. Sixty-nine (41%) of 169 patients receiving pegloticase developed high titer anti-pegloticase antibodies and

Figure 3. Hand tophi and sequential response to pegloticase ^{2,3}

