- o In rare cases in conditions (e.g. transplant, Systemic Lupus Erythematosus (SLE)) other than gout mycophenolate mofetil has been linked (incidence rate of 14.4 cases/100,000 person-years and 289/100,000 person-years respectfully) with a serious disorder of the brain known as Progressive Multifocal Leukoencephalopathy (PML). Following discontinuation of MMF patient conditions typically improve with marked reduction of weakness, and in follow-up MRI showed regression of lesions over the next 6 months. We will actively monitor participants and in the event of suspected diagnosis of PML, MMF will be withdrawn.
- Mycophenolate mofetil use is associated with increased risks of pregnancy loss and congenital malformations.

b. Pegloticase (Infusion)

i. Immediate Risks

It is common for potent urate lowering therapies to lead to acute attacks of gout. Other uncommon symptoms reported in at least 5% patients treated with pegloticase that may occur during the study period are ecchymoses, sore throat, constipation, chest pain, and vomiting. Serious allergic reactions may happen in some people while receiving infusion of pegloticase. These infusion reactions can be serious and usually happen within 2 hours of the infusion. Chest discomfort (15%), flushing (12%), and dyspnea (11%) are the most common symptoms. Symptoms associated with pegloticase infusion resolve with slowing, interrupting, or stopping the infusion. 91% of these symptoms occur in patients with serum urate concentrations greater than 6 mg/dL. Therefore, all participants serum urate will be checked prior to infusion and any participant with 2 or more serum urate test > 6 mg/dL (following initial infusion) will not be infused and will be removed from the study. Symptoms associated with infusion reactions include:

- Hemolysis; Individuals with G6PD deficiency are excluded from the study
- O Join pain 14%; Pain following injection. Pain subsides over time
- o Difficulty breathing 14%; Subsides over time
- Muscle spasms 14%; Subsides over time
- o Nausea 9%; Subsides over time
- Fever 14%; Subsides over time
- Back pain 14%; Subsides over time
- Diarrhea 14%; Subsides over time
- Erythema 14%; Subsides over time
- Hypersensitivity 14%; Subsides over time
- Rash 29%; Subsides over time
- Pain/bruising at the infusion site; Pain following injection and bruising will subside over time.

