4 OBJECTIVES AND ENDPOINTS

OBJECTIVES	ENDPOINTS	JUSTIFICATION FOR ENDPOINTS
Primary		
To assess efficacy of daily mycophenolate mofetil (MMF) to attenuate immunogenicity to pegloticase.	Proportion achieving and maintaining serum urate ≤ 6 mg/dL through 12 weeks, compared to concurrent controls.	Serum urate ≤ 6 mg/dL is slightly below the urate solubility threshold and this threshold has been the accepted standard for nearly all modern gout trials. 23-26 If the serum urate goal is not maintained before or at the 12 week mark, it will be assumed that the participant has developed clinically relevant anti-pegloticase antibodies and they will receive no further infusions. This assumption and subsequent discontinuation of pegloticase is consistent with the protocol of large phase III randomized controlled trials and the product label.
To assess the incidence and types of adverse events/infusion reactions potentially associated with a dual therapy regimen of pegloticase and MMF.	Incidence and Type of Adverse Events (AEs), Serious Adverse Events (SAEs), and Participant withdrawals due to AEs, anaphylaxis, and Infusion Reactions (IRs)	Safety profile is important because of the addition of an immune modulatory agent (MMF) that has potential of causing serious AEs
Secondary		
To assess durability of immune modulation after discontinuation	Absolute change in serum urate from baseline to wk 24; week 12 to 24 Proportion of participants with serum urate < 6 mg/dL through week 24; week 12 to 24	Assess if the efficacy of the short course of MMF continues following discontinuation.
To identify and characterize pegloticase immune response by immunoglobulin	Anti-pegloticase antibody isotypes (IgG/IgM), specificity, and titers	We anticipate that the primary Ab produced will be IgM anti-pegloticase but some participants, who will likely be the non-

OBJECTIVES	ENDPOINTS	JUSTIFICATION FOR ENDPOINTS
		responders will produce
		both IgM and IgG
		antibodies at earlier onset
To assess patient reported outcomes	PROs using PROMIS and Gout Impact score	To assess impact of the
(PRO)		intervention on patient
		reported outcomes
Tertiary/Exploratory		
Not applicable		

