Following completion of Visit 11 participants will continue on pegloticase for an additional twelve weeks without immune modulating therapy to evaluate the longer term benefits of this approach. In Phase 2 participants will continue with pegloticase infusions every 2 weeks.

Visit 12 (14 weeks)

- o Obtain and record vital signs, including pulse rate, blood pressure, and body temperature
- Targeted Physical Exam and joint assessment
- o Review / update concomitant medications
- Assess any AEs, and record
- Gout Flare assessment
- Laboratory Assessments
 - CBC with diff
 - sUA
 - Pregnancy test for premenopausal women
 - CMP
- Gout Flare Prophylaxis
- IR Prophylaxis / Assess for IRs
- Administer pegloticase infusion, per site guidelines.

Visit 13 (16 weeks)

- Obtain and record vital signs, including pulse rate, blood pressure, and body temperature
- Targeted Physical Exam and joint assessment
- Review / update concomitant medications
- o Assess any AEs, and record
- Gout Flare Assessment
- PROs (PROMIS-29 & GIS instrument)
- Laboratory Assessments
 - CBC with diff
 - sUA
 - Pregnancy test for premenopausal women
 - CMP
- Gout Flare Prophylaxis
- o IR Prophylaxis / Assess for IRs
- Administer pegloticase infusion, per site guidelines

Visit 14 (18 weeks)

- Obtain and record vital signs, including pulse rate, blood pressure, and body temperature
- o Targeted Physical Exam and joint assessment
- Review concomitant medications, and record

- Assess any AEs, and record
- Gout Flare Assessment
- Laboratory Assessments
 - CBC with diff
 - SUA
 - Pregnancy test for premenopausal women
 - CMP
 - Pegloticase Antibody/Mechanistic Study
- Gout Flare Prophylaxis
- IR Prophylaxis /Assess for IRs
- Administer pegloticase infusion, per site guidelines

Visit 15 (20 weeks)

- o Obtain and record vital signs, including pulse rate, blood pressure, and body temperature
- o Targeted Physical Exam and joint assessment
- o Review concomitant medications, and record
- Assess any AEs, and record
- Gout Flare assessment
- o PROs (PROMIS-29 & GIS instrument)
- Laboratory Assessments
 - CBC with diff
 - sUA
 - Pregnancy test for premenopausal women
 - CMP
- Gout Flare Prophylaxis
- o IR Prophylaxis / Assess for IRs
- Administer pegloticase infusion, per site guidelines

Visit 16 (22 weeks)

- Obtain and record vital signs, including pulse rate, blood pressure, and body temperature
- Targeted Physical Exam and joint assessment
- o Review concomitant medications, and record

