One of the primary objectives of this feasibility pilot study is to determine if there is an overall reduction in immunogenicity leading to increased responders to pegloticase when MMF is co-administered in adults with chronic refractory gout. We have developed a decision table (see Figure 4) indicating when we will have sufficient evidence to move forward to a full scale clinical trial. Figure 4 compares the success rates in the peg+MMF arm (N=24) versus peg+PBO (N=8). The area in green is the area that we will lead us to recommend continuing to test the treatment approach in a full scale study assuming safety. This green area represents the area that achieves a significant (2 tailed p < 0.10) Fisher's exact test that peg+MMF is better than pegloticase alone. The yellow area represents an achievement of a 2-tailed p < 0.25. If the results end up in the yellow or red areas, we will examine the Ab assays to determine if there is a clear significant difference in immune response. Based on these sample sizes, the mean difference in Ab titer level needs to be at least 1 standard deviation unit apart to achieve 73% power. Nevertheless, this would be a large difference for a clinical outcome variable, but for a marker such as Ab titers this is not unreasonable. Should the titer distributions not be consistent with normality assumptions, nonparametric analyses using a Wilcoxon test will be used, since the titer levels are already measured on a log scale precluding a simple transformation to achieve normality. Participants before the 12 weeks primary endpoint that do not tolerate MMF, or are lost to follow-up, withdraw, or are otherwise not evaluable will be counted as failures but not non-responders in sensitivity analyses. MMF efficacy will be examined by the proportion of responders and tested against the control group rate using Fisher's exact test. Success rates of the efficacy primary outcome will be determined using summary statistics and 95% confidence intervals. In the event of missing antibody data, imputations will be considered to assure data completeness for our analyses using PROC MI and PROC MIANALYZE procedures with 5 replicates per value. All analyses will be conducted using SAS (V9.4, Cary, North Carolina).

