10.4.2 ANALYSIS OF THE PRIMARY EFFICACY ENDPOINT(S)

MMF efficacy will be examined by the proportion of responders and tested against the control group rate using Fisher's exact test. Success rates of the efficacy primary outcome will be determined using summary statistics and 95% confidence intervals. As stated in section 10.4.1, should the success rates fall within the green area of **Figure 4** we will recommend testing in a larger study assuming safety and a demonstrated effect on Ab titers, our presumed intervening variable. We will examine failures and responders descriptively and via graphical methods.

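### The plan does not say which urate rule defines a responder, so a first value above 6 mg/dL at week 12, or an isolated earlier one, can be scored either way

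*Combined protocol and SAP*

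**What the plan says.** Three places describe loss of urate response.

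- **Section 4**, which carries the endpoint repeated in sections 2.1, 5.1, 9.1 and 10.1, gives no count and no confirmation step: "If the serum urate goal is not maintained before or at the 12 week mark, it will be assumed that the participant has developed" (the sentence goes on to name antibodies against pegloticase). Such a participant gets no further infusions.
- **Section 3.3.1** gives a count without requiring the values to be consecutive: "any participant with 2 or more serum urate test > 6 mg/dL (following initial infusion) will not be infused". The participant is then removed from the study.
- **Section 8.1** requires consecutive values: "participants with two consecutive serum urate levels above 6 mg/dL shall be classified as a non-responder and discontinued from the study".

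The analysis section adopts none of them by reference. Section 10.4.2 says "MMF efficacy will be examined by the proportion of responders and tested against the control group rate" with Fisher's exact test, and gives no definition of a responder. Figure 4 turns the two counts into a zone. Green is a two-tailed p below 0.10 favouring MMF, and yellow is a two-tailed p below 0.25. Table 1 has urate sampled before infusion at weeks 2, 4, 6, 8, 10 and 12, and next at week 14 (Visit 12).

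**The concern.** A statistician scoring the primary endpoint needs one rule that takes a participant's urate series to yes or no. For two patterns the text gives opposite answers.

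The clearer one is a first value above 6 at week 12. Section 4 says before or at that time point, so the participant has failed. Section 8.1 needs a second consecutive value, and the next scheduled sample falls at week 14, outside the endpoint window. The other is a single value above 6 earlier on, with later values back at or below 6.

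If the rule is still open when the data are unblinded, the definition could be chosen knowing which zone of Figure 4 it gives. That zone is the stated efficacy criterion for recommending a full-scale trial.

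**Working it through.** **1. Scoring by reading**

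| Urate pattern after first infusion | Section 4, read literally | Section 3.3.1 | Section 8.1 |
|---|---|---|---|
| Two consecutive values > 6 | fails | fails | fails |
| Two non-consecutive values > 6 | fails | fails | not a non-responder |
| One isolated value > 6 before week 12 | fails | does not fail | not a non-responder |
| First value > 6 at week 12 | fails | does not fail | not a non-responder by week 12 |

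**2. Figure 4 reproduced**

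With m successes in total, a table with a successes on MMF has probability C(24,a) × C(8,m−a) / C(32,m). The two-sided p sums the tables no more probable than the observed one. This gives 0.081 for 8 v 0 and 0.25 for 24 v 7, matching the printed 0.08 and 0.25.

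**3. One participant re-scored**

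- 21/24 v 4/8 (m = 25): (141,680 + 15,456 + 672 + 8) / 3,365,856 = 0.047, green.
- 20/24 v 4/8 (m = 24): the upper tail is (743,820 + 113,344 + 7,728 + 192 + 1) / 10,518,300 = 0.082. The opposite table, 16/24 v 8/8, has weight 735,471, below the observed 743,820, so it is added. Total 1,600,556 / 10,518,300 = 0.152, yellow.
- The same calculation gives 19/24 v 4/8 = 0.176 (yellow) and 19/24 v 3/8 = 0.072 (green). Re-scoring one placebo participant thus moves the result into green.

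**4. How often it could matter (illustration only)**

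The documents give no rate of isolated values above 6. Assume:
- a chance e of 1% or 5% per sample in a participant with sustained response, independent between samples;
- the six pre-infusion samples at weeks 2 to 12, all taken;
- true success rates of 80% v 60% (section 10.2), with the same rule in both arms.

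Share of sustained responders scored as failures:

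| Rule | Formula | e = 1% | e = 5% |
|---|---|---|---|
| Two consecutive | 1 − Σ C(7−k,k) e^k (1−e)^(6−k), k = 0 to 3 | 0.050% | 1.20% |
| Two consecutive, or week-12 value > 6 | 1 − (1−e) × Σ C(6−k,k) e^k (1−e)^(5−k), k = 0 to 3 | 1.04% | 5.91% |
| Two or more | 1 − (1−e)^6 − 6e(1−e)^5 | 0.146% | 3.28% |
| Any value | 1 − (1−e)^6 | 5.85% | 26.49% |

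Exact enumeration over both arms starts from the two-consecutive rule. The probability of green is then 24.3% at e = 1% and 23.5% at e = 5%.

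| Change from two consecutive to | P(green), e = 1% / 5% | Green status changes in, e = 1% / 5% |
|---|---|---|
| also failing an unconfirmed week-12 value | 23.6% / about 21% | 2.3% / 8.3% of trials |
| two or more | 24.2% / 22.2% | 0.2% / 4.4% |
| every sample ≤ 6 | 20.9% / 12.3% | 9.8% / 18.7% |

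The changes go both ways. In the last row at e = 5%, green is lost in 15.0% of trials and gained in 3.8%.

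The model leaves out the single-value check before each infusion (section 8.1) and possible withdrawal after one infusion period without treatment (section 8.2). Either could end a series after one value above 6.

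**The case against.** Sections 3.3.1 and 8.1 are stopping rules, whereas the endpoint has one wording throughout. Section 4 links loss of the goal to stopping infusions, and section 8.1 gives the count that triggers discontinuation and attaches the label non-responder. Read together, section 8.1 plausibly puts section 4 into operation. That is a fair reading and may be what is meant. It does not close the gap: section 10.4.2 does not point to section 8.1, and the two still disagree about week 12.

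Isolated values may also be rare. Section 3.2 describes loss of efficacy as "manifested by a rapid increase in serum urate levels in roughly 42% of all participants", which suggests sustained loss, on which all readings agree. The excursion rates above are assumed, and the largest figures depend on the literal any-value reading. The one-participant flips reflect small arms and a threshold; they do not show that such a participant is likely. All of this stands and limits the size of the point.

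The decision does not hang on p alone. Yellow or red leads to review of the antibody assays (section 10.4.1), green also requires safety and an effect on antibody titres (section 10.4.2), and section 10.4.3 calls the primary and secondary analyses descriptive. That softens the consequence but does not supply the missing rule.

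**Conclusion.** The point holds in a limited form. The plan cannot be followed as written for a first value above 6 at week 12 or for an isolated earlier value, and one such participant can change the Figure 4 zone in either direction. Under the assumed 1% to 5% excursion rates and true rates of 80% v 60%, the week-12 question alone changes green status in about 2% to 8% of trials. A literal every-sample reading would change it in about 10% to 19%. The difference between two or more and two consecutive values is small, at 0.2% to 4.4%.

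A reader might infer that the go decision is unreliable in nearly one trial in five, or that the ambiguity favours MMF. The documents support neither. The upper figure needs both an assumed 5% rate and the any-value reading, which section 8.1 may displace. The rule applies to both arms, so the direction in this trial cannot be predicted. Nor does the point undermine the scoring of sustained loss of response.

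**What to change.** Before unblinding, the sponsor should reconcile sections 3.3.1, 4 and 8.1 and state in section 10.4.2 the one responder rule used for the Fisher test and Figure 4. It should say:

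- whether one value above 6 or two consecutive values make a failure;
- how a first value above 6 at week 12 is scored, including whether the week-14 value may be used.

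The other reading should be reported as a sensitivity analysis with its Figure 4 zone. No view is taken here on which discontinuation rule is right.

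The cost is wording in the protocol and one extra analysis. No new samples are needed.
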